## 4. STATISTICAL CONSIDERATIONS

### Sample Size and Power

The sample size is based on feasibility. Our primary feasibility measures are participation, accrual, and retention rates. Anticipated participation and retention rates are based on pilot feasibility studies among YACS and our previous work with this population. With an estimated participation rate of 85% (consistent with CO-I's experience, LCCC 1707), we anticipate it will be feasible to recruit 80 YACS within 6 months. We will test the null hypothesis that the proportion recruited is 50% or lower versus the alternative that it is 65% or greater using a one-tailed test at an alpha level of 0.05 with 95% power, which would support that the study is feasible.

We plan to accrue no more than 100 participants looking to have at least 80 evaluable participants, for 5 participants in each of the 16 groups. We expect accrual to take a total of 10 months at a rate of approximately 10 participants per month. We anticipate accruing 80 participants within 10 months, or 12-15 participants per month. A sample size of 80 achieves 99% power to detect a difference between a null hypothesis mean accrual rate of 12 participants/month and an alternative hypothesis mean of 15 participants/month with a significance level of 0.05 using a one-sided one-sample Poisson test.

For retention, we will test the null hypothesis that the retention is 70% or below versus the alternative that the retention is 90% or greater using a one-tailed test at a 0.05 alpha level. With 80 participants we would reject the null hypothesis that the retention is 70% if at least 62 participants are retained with 90% power, which would support that the study is feasible. With 80 participants we would reject the null hypothesis that the retention is 70% if at least 66 participants are retained with 97% power, which would support that the study is feasible.

All three endpoints must meet the proscribed criteria in order for the study to have successfully demonstrated feasibility.

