### Statistical Analysis

Primary Endpoint Analysis. *Accrual rate* will be defined as the number of YACS who agreed to participate divided by the number of weeks of recruitment. *Participation rate* will be defined as the percent of eligible participants who agreed to participate. *Retention rate* will be defined as the number of participants who completed 3-month measures divided by the number who consented to participate. Means and 95% confidence intervals will be computed for all rates. The proportion of patients who complete the 3-month assessment will be reported along with an exact 95% confidence interval. This percentage will also be reported for experimental condition individually. We will test the hypothesis that the recruitment rate is  $\leq 50\%$  vs.  $\geq 65\%$  using a one-sample test of proportions with a one-sided alpha level of 0.05. We will test the hypothesis that the retention rate is  $\leq 70\%$  vs.  $\geq 90\%$  using a one-sample test of proportions with a one-sided alpha level of 0.05. We will use a one-sample Poisson test to compare the average number of participants accrued per month with a null hypothesis of 12 participants per month and a one-sided alternative of 14 participants per month at an alpha level of 0.05.

Secondary Endpoint Analysis. Ratings of program acceptability and satisfaction will be summarized using descriptive statistics (mean, standard deviations, frequencies) of the post-treatment evaluation (Objective 2.1.3). Descriptive statistics (percentages, medians, interquartile ranges) will be used to estimate adherence to daily self-monitoring (Objective 2.1.4), and study measures relating to demographics, anthropometric, clinical, behavioral, and psychosocial measurements (Objectives 2.1.5-2.1.7.). These study measures will be reported at baseline and 3 months. We will also estimate changes in weight, anthropometric, clinical, behavioral, and psychosocial measures from baseline to 3 months, and within each experimental condition, the change scores

will be tested to see if they are significantly different from 0 using Wilcoxon Signed Rank tests.

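### The 99% power stated for the accrual test (12 versus 15 per month, 80 participants) should be about 60–62%, and the null of 12 per month exceeds one of the plan's own accrual forecasts

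*Combined protocol and SAP*

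**What the plan says.** Everything here is in section 4 of the combined protocol and SAP unless noted.

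- **Power claim** (Sample Size and Power): "A sample size of 80 achieves 99% power to detect a difference between a null hypothesis mean accrual rate of 12 participants/month". The sentence goes on to an alternative of 15 per month, one-sided, at 0.05.
- **Analysis of the same test** (Statistical Analysis): "null hypothesis of 12 participants per month and a one-sided alternative of 14 participants per month at an alpha level of 0.05".
- **Size**: "We plan to accrue no more than 100 participants looking to have at least 80 evaluable participants". The section opens with "The sample size is based on feasibility".
- **Forecasts** (Sample Size and Power): "we anticipate it will be feasible to recruit 80 YACS within 6 months"; then "We expect accrual to take a total of 10 months at a rate of approximately 10 participants per month"; then "We anticipate accruing 80 participants within 10 months, or 12-15 participants per month".
- **Decision rule**: "All three endpoints must meet the proscribed criteria in order for the study to have successfully demonstrated feasibility".

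Three further figures bear on the test. The synopsis lists 72 subjects. The informed-consent text in section 5 gives a recruitment period of 30 months. The Statistical Analysis section defines the accrual rate per week but tests it per month.

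**The concern.** A Poisson rate test draws its information from the number of events, here the participants accrued. Separating 12 from 15 per month with about 80 events is hard: 80 participants at 15 per month take 5.33 months, in which 12 per month would give 64. The gap of 16 is two null standard deviations (√64 = 8), far too little for 99% power.

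The null also looks misplaced. A feasibility null is normally a floor that the team expects to beat, yet one forecast in the same section, about 10 per month, lies below it.

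Because the three criteria are joined, the power of the accrual test caps the chance of declaring the pilot feasible, however good participation and retention are. A reader who trusts the 99% would blame a failed accrual test on poor recruitment, when it could easily be chance or a null set above the forecast.

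**Working it through.** **Inputs.** Null 12 per month; alternative 15 (power statement) or 14 (analysis section); one-sided alpha 0.05; N = 80, cap 100, synopsis figure 72. The plan does not say whether the test uses the time to the Nth participant or the count in a fixed window, so both were run.

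**1. Time to the Nth participant.** If accrual is Poisson with rate λ, then 2λT follows chi-square with 2N degrees of freedom. The null is rejected if T ≤ t, where t = χ²(0.05; 2N) / (2 × 12). Power is P(χ² with 2N df ≤ 2λt).

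- N = 80: t = 131.76 / 24 = 5.490 months, an observed rate of at least 80 / 5.490 = 14.6 per month. At λ = 15: 2 × 15 × 5.490 = 164.7, power **0.617**.
- N = 100: t = 168.28 / 24 = 7.012 months; power 0.706 at 15 and 0.440 at 14.
- N = 72: t = 4.886 months; power 0.576 at 15.

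**2. Exact count in a fixed window.** Reject if X ≥ c, with c the smallest count for which P(X ≥ c) ≤ 0.05 under a Poisson mean of 12 × months.

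| Window (months) | Cut-off c | Power at 15 | Power at 14 |
|---|---|---|---|
| 80/15 = 5.33 | 78 | 0.603 | 0.365 |
| 80/14 = 5.71 | 83 | 0.630 | 0.383 |
| 6 | 87 | 0.638 | 0.386 |
| 100/15 = 6.67 | 96 | 0.669 | 0.405 |
| 7 | 100 | 0.700 | 0.433 |
| 10 | 139 | 0.826 | 0.545 |

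The 10-month window cannot be used: its cut-off of 139 is above the cap of 100. The 7-month window, where the cut-off equals the cap, gives 70%. For the 72 in the synopsis (72/15 = 4.8 months, cut-off 71), power is 0.563.

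**3. Can 99% be reproduced?** Not with 80 participants. For the 5.33-month window, a score approximation gives 62.5%, a square-root transform 59.6% and a Wald form 55.7%. In the time-to-Nth form, 99% needs about 314 participants, with a rejection limit of 23.8 months. In the fixed-window form it needs about 24 months (cut-off 317, power 0.990), in which 15 × 24 = 360 participants are expected. Reading 80 as months of observation (960 versus 1,200 participants; cut-off 1,012) gives over 99.9%. That may be where the figure came from, but this is conjecture.

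**4. Chance of passing at the plan's own rates** (time to the 80th participant):

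| True rate per month | Source | P(pass) |
|---|---|---|
| 10 | forecast of about 10 | 0.001 |
| 12 | null; low end of 12–15 | 0.050 |
| 13.3 | 80 in 6 months | 0.228 |
| 14 | alternative, analysis section | 0.375 |
| 15 | alternative, power statement | 0.617 |

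**5. One-sided p-values if accrual goes exactly as stated**, P(X ≥ n) with mean 12 × months:

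| Outcome | p |
|---|---|
| 80 in 10 months | > 0.99 |
| 100 in 10 months | 0.97 |
| 80 at 10 per month (8 months) | 0.96 |
| 80 at 12 per month (6.67 months) | 0.51 |
| 80 in 6 months | 0.19 |
| 80 at 14 per month (5.71 months) | 0.096 |
| 80 at 15 per month (5.33 months) | 0.030 |

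Only the last outcome passes.

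**6. Forecasts side by side.** 80 in 6 months is 80/6 = 13.3 per month. 80 in 10 months is 8 per month, yet the same sentence equates it with 12–15. 100 in 10 months is 10 per month. The 30 months in the consent text would make 80 participants 2.7 per month.

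**The case against.** The best defence concerns the null. The plan does not settle on 10 per month: it also gives 12–15 per month and 80 in 6 months. The Recruitment section reports 280 participants in 14 months in the team's earlier trial, or 20 per month, a rate at which the 80th participant would arrive in time about 99.9% of the time. On that view the documents hold contradictory forecasts and do not show a null above a settled expectation. This stands in part: the conflict has to be resolved before anyone can say whether 12 is too high. But the 10-per-month forecast is in the plan's own text, and a true rate of 12, the low end of the range, passes only 5% of the time.

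Second, 60–62% depends on an unstated observation period, and the number accrued may exceed the 80 evaluable. That is right, and it is why ranges are given; no period compatible with the cap of 100 gets above about 71%.

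Third, the 99% figure does not drive the sample size, and 14 versus 15 does not alter the rejection rule, which depends only on the null and alpha. Both are true. The power statement still misdescribes a primary criterion that can fail the study on its own.

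**Conclusion.** The concern holds. For 12 versus 15 per month at one-sided 0.05, power with 80 participants is about 60–62% (67–71% at the cap of 100; 56–58% at 72), against the stated 99%. With 14 as the alternative it is about 37–38% with 80 and 40–44% with 100. At a true 15 per month the accrual criterion, and so the feasibility claim, is missed about 38–40% of the time with 80 participants.

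The null of 12 is above the forecast of about 10 per month, and accrual exactly as the plan describes it mostly fails the plan's own test. How serious the null is depends on which forecast the investigators stand by.

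The figures assume Poisson accrual at a constant rate, participants as the events, and no more than 100 accrued.

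**What to change.** 1. State whether the accrual test uses the time to the Nth participant or the count in a fixed window, with the N or the window, and the unit (week or month).
2. Replace the 99%. For the time-to-Nth form with 12 versus 15, write about 62% at 80 participants (about 71% at 100). If 14 is the intended alternative, write about 37% (44% at 100). If another form is chosen, recompute for it.
3. Use one alternative in both Sample Size and Power and Statistical Analysis.
4. Reconcile the durations (6, 10 and 30 months), the rates (about 10 versus 12–15 per month) and the totals (72, 80 and up to 100).
5. Then check that the null is a minimum acceptable rate lying below the reconciled forecast. Its value is for the investigators to set.

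Items 2 to 4 are text corrections that need no new data; the stated power becomes less favourable. Item 1 settles an open detail of a primary test, and any change under item 5 alters a primary decision rule, so both should be made and documented before accrual data are analysed.

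### The retention test is given two different rejection cut-offs (62 and 66 of 80), and the 62 cut-off exceeds the stated one-sided 5% alpha

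*Combined protocol and SAP*

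**What the plan says.** Section 4, Sample Size and Power, sets up one retention test: "we will test the null hypothesis that the retention is 70% or below versus the alternative that the retention is 90% or greater". The test is one-sided with alpha 0.05. Two consecutive sentences, alike except for their numbers, then give its rejection rule:

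- "With 80 participants we would reject the null hypothesis that the retention is 70% if at least 62 participants are retained with 90% power";
- reject "if at least 66 participants are retained with 97% power", also with 80 participants.

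Nothing marks either as an alternative, a sensitivity rule or a superseded figure. The subsection ends: "All three endpoints must meet the proscribed criteria in order for the study to have successfully demonstrated feasibility".

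Section 4, Statistical Analysis, repeats the hypotheses and says they will be tested "using a one-sample test of proportions with a one-sided alpha level of 0.05". It does not say whether the test is exact or approximate, and it gives no cut-off. It defines retention as the "number of participants who completed 3-month measures divided by the number who consented to participate".

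**The concern.** One test with one sample size, null, side and alpha has one cut-off once the version of the test is chosen. Here there are two, four participants apart, and the powers attached to them run the wrong way: the stricter rule is credited with 97% and the looser with 90%. That alone shows that at least one sentence is wrong, before any calculation.

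Retention is a primary feasibility measure and a necessary condition for declaring the study feasible. If the final count falls between the two cut-offs, the conclusion depends on which sentence is followed. A choice made after the count is known would be post hoc.

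**Working it through.** **Inputs** (all from section 4): n = 80, p0 = 0.70, p1 = 0.90, one-sided alpha 0.05, written cut-offs k = 62 (stated power 90%) and k = 66 (stated power 97%).

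**Exact size and power.** With X ~ Binomial(80, p), size is P(X ≥ k | p = 0.70) and power is P(X ≥ k | p = 0.90).

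| Cut-off k | k/80 | Size at 70% | Power at 90% | Power stated |
|---|---|---|---|---|
| 62 | 77.5% | 0.0873 | 0.9997 | 90% |
| 63 | 78.75% | 0.0531 | 0.9992 | – |
| 64 | 80.0% | 0.0302 | 0.9979 | – |
| 65 | 81.25% | 0.0161 | 0.9947 | – |
| 66 | 82.5% | 0.0079 | 0.9877 | 97% |
| 67 | 83.75% | 0.0036 | 0.9733 | – |

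The first sentence is not reproduced in either respect: its size exceeds 0.05 and its power is not 90%. The second holds alpha, and its power is within 2 points of the stated 97%. The smallest cut-off that keeps exact size at or below 0.05 is 64.

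**Could another version of the test give 62?** The analysis section does not name the version, so the usual ones were tried. Under the null, the mean is 80 × 0.70 = 56 and the SD is √(80 × 0.70 × 0.30) = √16.8 = 4.099. One-sided p-values at 62 retained:

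- z, null variance: (62 − 56)/4.099 = 1.464, p = 0.072
- z, continuity-corrected: (61.5 − 56)/4.099 = 1.342, p = 0.090
- Wald, estimated variance: 0.075/√(0.775 × 0.225/80) = 1.606, p = 0.054
- mid-p: (0.0873 + 0.0531)/2 = 0.070
- likelihood ratio: p = 0.066
- arcsine: p = 0.063

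None rejects at 0.05. The uncorrected z-test needs at least 56 + 1.645 × 4.099 = 62.74, so 63 (p = 0.044, exact size 0.053). The corrected z-test needs 63.24, so 64 (p = 0.034).

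**Where the figures might come from.** A cut-off of 62 is the exact cut-off at one-sided 0.10 with n = 80 (0.0873), or at 0.05 with n = 78 (0.0406). The text states neither setting. The 62 rule has 90% power only if true retention is about 82.4%, a value the protocol does not give. The 97% figure matches at least 67 (0.973), so a slip between at least 66 and more than 66 is possible. These are guesses at the origin and the conclusion does not need them.

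**How often the two rules disagree.** P(62 ≤ X ≤ 65) = P(X ≥ 62) − P(X ≥ 66):

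| True retention | P(X ≥ 62) | P(X ≥ 66) | Rules disagree |
|---|---|---|---|
| 70% | 0.0873 | 0.0079 | 0.079 |
| 75% | 0.3563 | 0.0740 | 0.282 |
| 80% | 0.7621 | 0.3463 | 0.416 |
| 85% | 0.9741 | 0.7874 | 0.187 |
| 90% | 0.9997 | 0.9877 | 0.012 |

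**Denominator.** Both counts assume 80. The analysis divides by the number consented, and accrual of up to 100 is allowed. Taken literally with 100 consented, 62 or 66 retained would be 62% or 66%, both below the null. The exact 5% cut-off at n = 100 is 78 (size 0.048).

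**The case against.** The strongest reply is that Statistical Analysis already fixes the decision: it states the null, the alternative, the side, the alpha and the kind of test. The counts appear only in the sample-size text, where a cut-off usually illustrates the test. An analyst who follows the analysis section would compute a p-value and use neither count, and the 8.7% false-pass rate would not arise. On that reading the 62 sentence also misleads over a narrower range: only at 62 or 63 retained under the exact test, and only at 62 under the uncorrected z-test.

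It is also true that the two rules rarely disagree at the planned 90% retention (0.012), that this is a low-risk behavioural pilot with no efficacy decision resting on the criterion, and that the retention proportion will be reported with an exact 95% interval in any case.

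These points limit the consequence but do not remove the error. Both sentences are worded as rejection rules, and the all-three-endpoints sentence does not say whether its criteria are the tests or the counts. Even if the test governs, the 62 sentence misreports what that test would conclude. Disagreement is most likely at 75% to 85% retention, between the null and the alternative, where a decision rule has most work to do. The choice of 64 over 63 depends on the version of the test, which is a reason to name it.

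**Conclusion.** The point holds. The protocol gives two incompatible cut-offs for one co-required primary criterion. The 62 cut-off breaches the protocol's own alpha under all six alternatives to the exact test that were tried (0.054 to 0.090) as well as under the exact test (0.087), and its stated power is wrong (99.97%, not 90%). The 66 cut-off is valid but conservative (exact size 0.008, power 98.8%). Neither is the 5% cut-off, which is 64 by the exact or continuity-corrected test and 63 by the uncorrected z-test. These results assume n = 80, independent participants and the hypotheses as written. The practical effect depends on true retention: the chance of a result on which the rules disagree runs from about 1% at 90% retention to about 42% at 80%.

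**What to change.** Before 3-month retention is known, replace the two sentences with one that gives a single cut-off, names the test, and states its actual size and power. Two options:

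- exact binomial, at least 64 of 80: size 0.030, power 99.8% at 90% retention;
- if a stricter bar is intended, at least 66 of 80: size 0.008, power 98.8%.

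Delete the 62 rule. Name the same test under Statistical Analysis, and say whether the criteria that must all be met are the tests or the counts. Add that the test is applied to the actual number consented if that is not 80 (for example, at least 78 of 100 by the exact test, size 0.048).

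The cost is an edit to the protocol and analysis text. Sample size, data collection and the reported estimate do not change.

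### Feasibility needs all three tests to succeed, but power is printed only for each test alone; the three-way rule has about 58–61% power at 80 participants, almost wholly because the accrual test is weak

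*Combined protocol and SAP*

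**What the plan says.** Section 4, Sample Size and Power, bases the sample size on feasibility and sets three one-sided tests at 0.05.

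- **Participation.** "We will test the null hypothesis that the proportion recruited is 50% or lower versus the alternative that it is 65% or greater". The claimed power is 95%, and rejecting the null is said to support feasibility. Statistical Analysis says the rate "will be defined as the percent of eligible participants who agreed to participate", but neither section gives the expected number of eligible people.
- **Accrual.** A one-sample Poisson test of 12 against 15 per month, with 99% power claimed for 80 participants. Statistical Analysis repeats the test with "a one-sided alternative of 14 participants per month at an alpha level of 0.05".
- **Retention.** 70% against 90%, with two cut-offs out of 80: at least 62 with 90% power, and then "if at least 66 participants are retained with 97% power, which would support that the study is feasible".

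The section closes with the decision rule: "All three endpoints must meet the proscribed criteria in order for the study to have successfully demonstrated feasibility". Neither the synopsis nor Section 4 gives a power for that rule.

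**The concern.** Feasibility is the primary objective, so the figure that matters is the chance that the three-way rule succeeds when the study really is feasible. A reader of the section sees 90–99% and takes the risk of wrongly missing feasibility to be 1–10%. Each of those figures describes one test, and a rule that needs all three cannot do better than its weakest part. If one part is much weaker than printed, the verdict is weaker still, and a failure to demonstrate feasibility would say less about the programme than the section implies.

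**Working it through.** **1. Printed figures taken as correct.**

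- Independent tests: 0.95 × 0.99 × 0.90 = 84.6%; 0.95 × 0.99 × 0.97 = 91.2%.
- Any dependence: the lower bound is the sum of the powers minus 2, and the upper bound is the smallest power. With retention at 90%: 0.95 + 0.99 + 0.90 − 2 = 84.0%, up to 90%. With retention at 97%: 0.95 + 0.99 + 0.97 − 2 = 91.0%, up to 95%.

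**2. Each test recomputed.**

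*Retention* (exact binomial, n = 80, null 0.70, alternative 0.90):

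| Cut-off | Type I error | Power | Printed power |
|---|---|---|---|
| 62 | 0.087 | 99.97% | 90% |
| 64 | 0.030 | 99.8% | not given |
| 66 | 0.008 | 98.8% | 97% |

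The cut-off of 62 does not hold the 0.05 level. The smallest that does is 64 (63 gives 0.053). The 90% is not reproduced; the 97% is close.

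*Participation* (exact binomial, null 0.50, alternative 0.65). If 80 consent at 65%, about 80 / 0.65 = 123 people are eligible. The cut-off is then 72 and the power 94.4%, which fits the printed 95%. With 94 eligible (80 / 0.85) the power is 88.6%.

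*Accrual.* If recruitment stops at N consents, the time to the Nth consent is gamma distributed with shape N. The test rejects when that time is below the 5% point under 12 per month: 5.49 months for N = 80 and 7.01 months for N = 100.

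| Design | Power at 15 per month | Power at 14 per month |
|---|---|---|
| Stop at 80 | 61.7% | 37.5% |
| Stop at 100 | 70.6% | 44.0% |
| Fixed 6 months | 63.8% | 38.6% |
| Fixed 10 months | 82.6% | 54.5% |

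The printed 99% is not reproduced. Reading 80 as a number of monthly counts gives about 100%, but would mean 80 × 12 = 960 to 80 × 15 = 1,200 participants. Ten months at 15 per month is 150 participants, above the plan's cap of 100.

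**3. The three-way rule, recomputed** (retention cut-off 64 of 80).

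- *Independent, 123 eligible, stop at 80, 15 per month:* 0.617 × 0.944 × 0.998 = 58%. At 14 per month: 0.375 × 0.944 × 0.998 = 35%.
- *One stream.* Each eligible person consents with probability 0.65 until 80 have consented, so slow accrual and low participation tend to occur together. In 400,000 simulated trials all three tests succeed in 61.3% at 15 per month and 37.4% at 14.
- *Stop at 100.* With 154 eligible (100 / 0.65), participation power is 98.2% and retention power (cut-off 78) is 99.99%. Independent: 0.706 × 0.982 × 0.9999 = 69%. One stream: 70.7%. At 14 per month: 43% and 44%.

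**4. Where the loss arises.** In the one-stream case at 80, accrual alone has 61.7% and all three together 61.3%. The combination costs about 0.4 points; the rest is the accrual test. Using the cut-off of 66 instead of 64 hardly matters: 0.617 × 0.944 × 0.988 = 57.5%.

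**The case against.** The best defence is that the section is open about its rule and never presents a single-test power as the power of the verdict. What is missing is a figure, and requiring all three successes does not inflate the type I error. That stands.

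Several stronger readings are tempting and are not supported.

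- *That 85–91% is a ceiling.* It is the product under independence, which the plan does not assert. The ceiling on the printed figures is 90% or 95%.
- *That requiring three successes is what brings power down to about 60%.* It is not. Participation and retention are both strong, and the fall is the accrual shortfall carried through.
- *That about 60% is the power of the plan as written.* The plan fixes neither the number eligible nor a stopping rule. It also names both 6 and 10 months for recruitment, while the informed-consent text in Section 5 says 30. At the expected 85% participation that test is almost certain to succeed, and the rule is then limited by accrual.
- *That the single-test sentences contradict the closing rule.* Each success can lend support while all three are needed to demonstrate feasibility. The wording invites misreading but can be reconciled.
- *That a failed verdict is bound to be over-read.* Statistical Analysis already promises confidence intervals for all rates, so readers will see which criterion failed and how precisely it was estimated.

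None of this supplies the missing figure or restores the 99%. The section also forecasts about 10 participants per month, below its own null of 12. At that rate, stopping at 80, the accrual test would reject about 0.1% of the time, and the three-way rule could do no better.

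**Conclusion.** The point holds as an unstated and much lower power for the primary decision. On the printed figures the three-way rule has about 85% or 91% under independence. Recomputed at 65%, 15 per month and 90%, it has about 58–61% stopping at 80 and about 70% stopping at 100; at 14 per month, about 35–37% and 43–44%. These rest on about 123 and 154 eligible people, a stop at the target count, and dependence between none and a single recruitment stream. A full 10 months at 15 per month would do better, but accrual alone limits it to 82.6% and it breaks the cap. So no reading that keeps within the cap delivers the 90% or more that the section conveys, and the accrual test is the reason.

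**What to change.** In Section 4:

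1. Replace the 99% accrual power with a figure computed for the actual number of participants (about 62% at 80, about 71% at 100, for 15 per month).
2. Use one accrual alternative (14 or 15) and one recruitment window throughout, and reconcile the forecast of 10 per month with the null of 12.
3. Keep one retention cut-off that holds the 0.05 level. Of the two printed, 62 does not.
4. After the closing rule, state the power of the three-way rule with its assumptions: number eligible, stopping rule, and dependence between accrual and participation.
5. Say that a single rejection counts towards feasibility but does not by itself demonstrate it.

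This is wording and recalculation only. The cost is a less favourable stated figure; no more patients are needed.
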